### 1.3 Exploratory Objectives

1.3.1. To examine potential differential effects of the intervention on anxiety, depression, sleep disturbance, fatigue, fear of recurrence, and QOL, by gender, age, race/ethnicity, rural v. urban status, stratification arm (moderate, severe), and psychotropic medication use at baseline.

1.3.2. To examine mediating effects of expectancy ratings of the intervention on anxiety and depression.

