### **7.6 Evaluation During Study Intervention**

**Weeks 1-12:**

- **High Intensity Week 1/Low Intensity Week 2:** The Expectancy Rating Scale and instructions (Appendix 10a/b) will only be mailed to participants who are randomized to either the Low Intensity or the High Intensity intervention groups. Participants are to complete this Expectancy Rating Scale after they have completed Chapter 1 of the Cognitive Behavior Therapy Workbook.

- Enhanced Usual Care participants will not be mailed the Expectancy Rating Letter or Scale.
- Enhanced Usual Care participants will be mailed a “Thank You” letter at baseline (Support Document 6).
- Stepped-Care Telehealth (High Intensity) Progress Notes (Appendix 16)/Session Information Form (session completed Y/N) (Entered by therapist or NCORP component research staff on study website within 48 hours of therapy or check-in sessions)
- Telephone Script/Manual for Low Intensity Bi-Weekly (every two weeks) Check-In Call Form (Appendix 14).
- Implementation costs (tracking logs) (Appendix 24)

**Week 7:** (visit must be completed between Week 6 and Week 11)

NCORP component research staff will administer the following mid-intervention assessments by telephone and enter in the study website (Appendix 11).

- PHQ-9
- GAD-7
- Current Medication Use (Update)
- Adverse Event Ascertainment Form
- Mid-intervention letter mailed to Enhanced Usual Care participants only (Support Document 6).

**7.7 Evaluation at Completion of Study Intervention – Week 13 (could occur weeks 13-15 only for High Intensity Participants):** (visit must be completed between Week 12 and Week 15)

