**Self-Administered Measures (Appendix 12a/b):**

Participants will be mailed the following self-report post-intervention measures with a request that they be returned within two weeks.

- Fear of Recurrence Inventory--Severity Subscale
- Insomnia Severity Index
- PROMIS Fatigue Scale- Short Form 8a
- SF-36 Health Survey
- Impact of Events Scale – Revised
- Client Satisfaction Questionnaire
- Working Alliance Inventory-Participant (high-intensity participants only)
- Expectancy Rating Scale (low intensity and high intensity participants only)

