## Study Parameter Table

	Recruitment/ Chart Review	Pre-Screen	Verbal Consent	Full Screen	Full Informed Consent	Baseline	Enrollment/ Randomization (wk0)	Weeks 1-13			Post Week 13
								Wk1 or 2	W7	W13	
NCORP Component Site Staff Responsibility											
Mail Recruitment Documentation*	As needed										---
Pre-Visit Form (Appx 2)	X										---
Pre-Screening Form (Appx 3)*		X a									---
Abbreviated Verbal Consent			X a								---
Screening Form (Appx 4)*				X a							---
Full Informed Consent					X a						---
Baseline Self-Report Letter and Measures (Appxs 5a+b)*						X a					---
Baseline Interviewer-Administered Measures and Chart Review (Appx 6)*							X a				---
Letter to Ineligible Participants (SD 2)		As Needed									---
Enrollment Form (Appx 7)							X				---
Randomization Form (Appx 8)							X b				---
EUC Randomization*							X		X		EUC
Expectancy Rating Scale and Letter  (Appxs 10a+b)							X				LISC/ HISC
Low Intensity Check-In Call Form (Appx 14)								Biweekly (wks 2/4/6/8/10/12)			LISC
Upload audio recordings								Biweekly (wks 2/4/6/8/10/12)			LISC
Week 7 Mid-Assessment Interviewer-Administered Measures (Appx 11)*									X		All
Week 13 Self-Report Letter and Measures (Appxs 12a+b)*										X	All
Week 13 Interviewer-Administered Measures (Appx 13)*										X c	All
Participant Completion Letter (SD 3)/Resource Sheet (SD 9)										X	LISC/ HISC
Participant Change Status Form (Appx 23)								As Needed			All
Adverse Event Form (Appx 22)		As Needed									All
Crisis Protocol Event Form (Appx 21)		As Needed									All
Tracking Log (Appx 24)		To be completed for each attempted contact and actual contact									All
Wake Forest Research Base Responsibility											
EUC Randomization*							X				EUC
Investigator adherence rating forms (Appx 18 and 19)*								As needed			LISC/ HISC
Mail Recorder							As needed				LISC/ HISC
Mail CBT Booklet							X				LISC/ HISC
Mail CBT Booklet										X	EUC
Study Therapist Responsibility											
Weekly Therapist activities (Appxs 15-17) recordings*								Weekly (wks 1-13)			HISC
Tracking log		To be completed for each attempted contact and actual contact									HISC

Abbreviations: Appx=Appendix, EUC=Enhanced Usual Care, HISC=High-Intensity Stepped-Care Arm, LISC=Low-Intensity Stepped-Care Arm

\* See appendix 26 for details

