### **13.2 Randomization/Stratification**

Participants will be stratified by baseline score  $\geq 15$  on the GAD-7 and/or on the PHQ-9, indicating severe anxiety or depressive symptoms, and by whether they qualified for the study by the GAD-7, PHQ-9, or both. Participants with moderate symptoms only (8-14 on the PHQ-9 and  $< 15$  on the GAD-7 or 10-14 on the GAD-7 and  $< 15$  on the PHQ-9) will be randomized to either the low-intensity stepped-care telehealth or to the enhanced usual care (EUC control) with equal probability. Participants with severe symptoms will be randomized to either the high-intensity stepped-care telehealth intervention or the EUC control with equal probability. Participants randomized to the low-intensity stepped care telehealth arm who experience increased symptoms at week seven and now experience severe level of symptomatology will receive the high-intensity intervention (see Section 7.1). Analysis will proceed as intent-to-treat using

their initial stepped-care telehealth assignment; we do not anticipate that many people will change from moderate to severe during the study. We anticipate enrolling 45 patients in the stepped-care telehealth intervention and 45 in the enhanced usual care group. We will enroll 50 participants in the moderate symptom strata, and 40 participants in the severe symptom strata. Block sizes will be chosen randomly to ensure that future assignments cannot be inferred from previous ones.

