### **13.6 Exploratory Objectives, Endpoints, Analysis Plans**

We will perform stratified subgroup analysis of the outcomes in Objectives 1.2.1 and 1.2.2. by gender, age, race/ethnicity, stratification arm (moderate, severe), and psychotropic medication use at baseline to meet Objective 1.3.1 using ANCOVA at week 13. To analyze Objective 1.3.2, we will use a mediation approach to examine whether expectancy ratings mediate the relationship between the intervention and the outcomes of interest (PHQ-9, GAD-7, or the combined outcome) at the intervention mid-point or end. First, we will examine whether the expectancy rating score is a significant predictor of the outcome in the mixed-model analysis of covariance (ANCOVA) model with terms for the expectancy rating score, baseline value of the outcome, therapist or site staff person conducting check-in calls, psychotropic medications use, a time effect (mid-, post-intervention), and the time by intervention expectancy score term (to test whether the expectancy score effects vary by time). Then we will fit the same model with the intervention effect, expectancy rating score, and their interactions with each other and time. If the effect for the mediator is significant in this model and the parameter estimate of the intervention effect is smaller than in the analysis of Objective 1.2.1 it will indicate evidence of mediation.

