### **13.7 Reporting and Exclusions**

Unless we receive written or verbal withdrawal of consent, we will try to reach every participant for telephone calls, telephone sessions, and assessments as outlined in the protocol.

The dataset used in the analysis of Objective 1.1.1 will include all eligible participants to calculate recruitment rates. Accrual, retention, and adherence will be calculated on the participants who consent to participate in the study. The analysis of the secondary objectives and exploratory objective will include all participants who consent to participate in the study. The ANOVA models used for the secondary objectives use data from all available time points and allows for data to be missing at random. For the analyses of the secondary objectives and the exploratory objective, we will use an intent-to-treat approach. If participants are moved from low intensity to high intensity they will be analyzed using the

low intensity assignment (intent to treat). In exploratory models, we will analyze the impact of adherence by including it as a predictor.

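### The mediation rule for Objective 1.3.2 cannot be evaluated, because the mediator is never measured in the enhanced usual care arm

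*Combined protocol and SAP*

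**What the plan says.** The objective, in Sections 1.3 and 13.1.3, is "To examine mediating effects of expectancy ratings of the intervention on anxiety and depression".

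Section 13.6 sets out two steps.

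- Step 1 asks whether the expectancy score predicts the outcome. The mixed model contains expectancy, baseline score, therapist or site staff, psychotropic medication use, time, and expectancy by time.
- Step 2 adds the intervention: "Then we will fit the same model with the intervention effect, expectancy rating score, and their interactions with each other and time". The verdict follows from this model: "If the effect for the mediator is significant in this model and the parameter estimate of the intervention effect is smaller than" it was in the Objective 1.2.1 analysis.

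Objective 1.2.1 (Sections 1.2 and 13.5) compares stepped care with EUC.

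On who completes the scale, three places agree:

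- Section 7.6, Weeks 1-12: "Enhanced Usual Care participants will not be mailed the Expectancy Rating Letter or Scale".
- Section 7.7, Week 13 self-administered measures: "Expectancy Rating Scale (low intensity and high intensity participants only".
- Study Parameter Table: the row "Expectancy Rating Scale and Letter" is marked for the low- and high-intensity arms only.

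On the analysis set, Section 13.7 states: "The analysis of the secondary objectives and exploratory objective will include all participants who consent to participate in the study".

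**The concern.** The step 2 rule needs a stepped-care-versus-EUC coefficient adjusted for expectancy. That requires expectancy values in both arms, and by design the EUC arm has none. The body of the protocol gives no EUC version of the scale, no rule for assigning EUC participants a value, and no restricted analysis set for this objective. Section 13.7 points the other way by including everyone who consents.

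The mediator is also not fully defined. The scale is completed at Week 1 or 2 and again at Week 13, and Section 13.6 does not say which rating is used. A Week 13 rating comes after the Week 7 outcome and alongside the Week 13 outcome, so it is a poor candidate for a mediator of either.

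At stake is whether a stated protocol objective can be answered. If the text stays as it is, software will drop the EUC records or the redundant terms, or someone will choose an EUC value after seeing the data. Either route could produce a mediation statement that the data cannot support, in a trial whose purpose is to inform a larger one.

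**Working it through.** The documents give no sample size or precision figure for Objective 1.3.2, so there is no stated number to reproduce. The check is whether the terms can be estimated.

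**Inputs**

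- Allocation, Section 13.2: 45 stepped care, 45 EUC.
- Strata, Section 13.2: "We will enroll 50 participants in the moderate symptom strata, and 40 participants in the severe symptom strata". Equal randomisation gives 50/2 = 25 low-intensity and 40/2 = 20 high-intensity.
- Outcome times, Section 13.5: two (mid- and post-intervention).
- Expectancy values: 0 in EUC, at most 45 in stepped care.
- Simplifications: intervention coded as stepped care versus EUC; therapist/staff term left out.

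**Ranks, using records with an expectancy value (45 × 2 = 90 rows)**

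Let A be the intervention (1 = stepped care), M expectancy and t time. In all 90 rows A = 1. Therefore A equals the intercept, A×M equals M, A×t equals t, and A×M×t equals M×t.

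| Model | Columns | Rank |
|---|---|---|
| Step 1: intercept, M, baseline, medication, t, M×t | 6 | 6 |
| Step 2: adds A, A×M, A×t | 9 | 6 |
| Step 2 with A×M×t | 10 | 6 |
| Step 2 with A×M×t, if M were measured in all 90 participants | 10 | 10 |

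Step 1 can be fitted, but only within stepped care. In step 2 no term involving A is estimable. The last row shows that the cause is the missing EUC measurement, not the form of the model.

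**Possible rescues**

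1. *Missing-data methods.* No EUC participant has any rating, so the EUC distribution would rest wholly on assumption.
2. *Giving EUC participants a fixed value.* Coding them 0 in the 10-column model gives rank 8: M is aliased with A×M, and M×t with A×M×t, so the mediator effect the rule must test is not estimable. Dropping the interaction restores estimability but makes the answer arbitrary. As an illustration with assumed values, take a true arm difference of -2, a stepped-care expectancy centred at 25 and a slope of -0.1. With EUC set to c, the coefficient of A is -2 - 0.1 × (c - 25) = 0.5 - 0.1c:

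| EUC value c | 0 | 10 | 20 | 25 | 30 | 40 |
|---|---|---|---|---|---|---|
| Coefficient of A | 0.5 | -0.5 | -1.5 | -2.0 | -2.5 | -3.5 |

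   Whether the estimate counts as smaller than the Objective 1.2.1 value of -2 is decided by c alone.

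3. *Reading the intervention as high versus low intensity.* Replacing A with a high-intensity indicator gives rank 10 of 10. But intensity is fixed by severity stratum (Sections 7.1 and 13.2), is not randomised, and is not the Objective 1.2.1 contrast.

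**What the data can support**

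A predictor model within stepped care (step 1 plus severity stratum) has rank 7 of 7. Adding intensity as well gives 7 of 8, because within stepped care intensity and stratum are the same variable.

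For a rough idea of precision, assume a correlation of 0.30 between rating and outcome. Fisher's z is atanh(0.30) = 0.310 with standard error 1/√(n - 3). The detectable correlation, at 80% power and two-sided 5%, is tanh[(1.96 + 0.84)/√(n - 3)].

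| Ratings available | Standard error | 95% CI around 0.30 | Detectable correlation |
|---|---|---|---|
| 45 (all returned) | 0.154 | 0.01 to 0.55 | 0.41 |
| 36 (20% loss, as allowed in Section 13.3) | 0.174 | -0.03 to 0.57 | 0.45 |

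The documents give no return rate for the scale. These figures also ignore covariates and repeated measures.

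**The case against.** The strongest reply is about consequence. The objective is exploratory, Section 13.8 says effect analyses are for planning and not for demonstrating efficacy, and an analyst would meet the non-estimable term at the first fit. It is true that no primary or secondary result is touched. But discovering the problem at analysis is the moment at which an arbitrary coding would be chosen, and the objective would still go unanswered.

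A second reply is that the rank result assumes a two-level intervention variable, whereas Section 13.5 compares each stepped-care group with EUC in the GEE analysis of the combined outcome. With low and high intensity as separate levels, a coefficient can be estimated. That qualification is right for the ranks. It does not save the rule, because the remaining contrast compares severity strata and not randomised arms.

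A third set of points concerns the replacement analysis, and these stand as cautions. It is imprecise, and the interval includes zero at 36 ratings. The rank check omits the therapist/staff term. Section 7.2 expects fewer than 10 participants per state, so a staff variance may be hard to estimate. A linear rank check also does not show that the binary combined outcome can be fitted with at most 45 people.

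**Conclusion.** The concern holds. Followed exactly, Section 13.6 cannot return a mediation verdict: the mediator exists for 0 of 45 EUC participants, and step 2 has rank 6 against 9 or 10 columns. The conclusion rests on the scale being limited to stepped care, as Sections 7.6 and 7.7 and the Study Parameter Table all state, and on the intervention meaning stepped care versus EUC, as the reference to Objective 1.2.1 requires. It does not depend on the illustrative values or on the return rate.

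The reach is limited to one exploratory objective. Step 1 remains usable within stepped care. The text should be corrected because a stated objective cannot be answered as written and the repair is cheap.

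**What to change.** Restate Objective 1.3.2 in Sections 1.3 and 13.1.3, and the matching text in 13.6, along these lines: within the stepped-care arm, examine whether the Week 1/2 expectancy rating predicts PHQ-9, GAD-7 and the combined outcome at Weeks 7 and 13, adjusting for baseline score and severity stratum.

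- Remove the intervention-by-expectancy term and the mediation rule.
- Say whether psychotropic medication use stays in the model; the 7-column check above includes it.
- Do not enter intensity as well as stratum.
- If the therapist/staff term is kept, make it a random effect. Therapists serve only the high-intensity group and site staff make only the low-intensity calls, so fixed effects would absorb the stratum. State what is done if the variance cannot be estimated.
- Name the model for the combined outcome; Section 13.5 already uses GEE with a logit link.
- Report estimates with 95% confidence intervals.
- In Section 13.7, state that this analysis is confined to stepped care. As a clarification only, say the same of the models using adherence as a predictor, since Section 5.2 defines adherence only for sessions and check-in calls.

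The cost is a wording change to a protocol objective, which means an amendment, plus edits to 13.6 and 13.7. No new data are needed. What is lost is the mediation claim. Keeping it would require an expectancy measure suited to EUC participants, and so new data collection.

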### **13.7 Reporting and Exclusions**

Unless we receive written or verbal withdrawal of consent, we will try to reach every participant for telephone calls, telephone sessions, and assessments as outlined in the protocol.

The dataset used in the analysis of Objective 1.1.1 will include all eligible participants to calculate recruitment rates. Accrual, retention, and adherence will be calculated on the participants who consent to participate in the study. The analysis of the secondary objectives and exploratory objective will include all participants who consent to participate in the study. The ANOVA models used for the secondary objectives use data from all available time points and allows for data to be missing at random. For the analyses of the secondary objectives and the exploratory objective, we will use an intent-to-treat approach. If participants are moved from low intensity to high intensity they will be analyzed using the

low intensity assignment (intent to treat). In exploratory models, we will analyze the impact of adherence by including it as a predictor.

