## 3. SUMMARY OF STUDY PLAN

This study compares a stepped-care telehealth intervention (tailored to level of symptomatology and designed to reduce anxiety and depressive symptoms) with enhanced usual care (EUC). Participants with no/mild symptoms will be provided survivorship resources and will not be included in the trial.

A total of 90 participants will be randomized. Study screening will be completed by a Research Nurse or an appropriate designated research staff member at each NCORP component. Assuming an accrual rate of approximately 8-9 randomized participants per month, we expect study recruitment to be complete within 11 months.

Referred participants will waive documentation of informed consent to complete the PHQ-2 and single anxiety question. If a participant scores  $\geq 2$  on the PHQ-2 or  $\geq 1$  on the anxiety question, he/she will be invited to complete the full screening assessment to determine study eligibility. The participant will complete the Abbreviated Verbal Consent at this point. We are asking to waive the following elements of

consent for this second step of screening: disclosure of appropriate alternatives, statements regarding who may access the participant's medical record for verification, and compensation for injury. If they meet all eligibility criteria and want to participate in the randomized trial, they will provide full informed consent for study participation. Trained research staff members at each NCORP component will obtain full informed consent from all interested and eligible potential participants.

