#### **7.4 Baseline Testing**

If full informed consent was administered by phone, the site must receive the signed full informed consent prior to initiating baseline study activities. Baseline Interviewer-Administered Measures and Chart Review must be administered and completed by site staff. Baseline Self-Administered Measures

may be completed by the participant at the site or site staff may choose to mail baseline self-administered measures to the participant with a request that they be returned as soon as possible and within two weeks (see Section 7.2). If the self-administered measures are mailed to a participant, site staff may call the participant to collect self-administered baseline responses by phone. Randomization must happen after baseline assessments but within 30 days of screening. Replacement packets can be mailed or emailed at participant request. The sites must receive the following self-administered completed forms from the participant prior to enrolling and randomizing the participant.

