### **7.5 Participant Enrollment and Randomization**

The electronic participant enrollment form (Appendix 7) will be completed on the day of randomization in the Telehealth study website. The subject should not be randomized and enrollment form completed until the subject is ready to start the intervention. Review the Appendix 5a/5b (Baseline Self-Report Measures) for completeness before randomization. Once the participant is randomized, the study timeline begins. A participant will not be considered enrolled if they are not randomized to a study arm. Following randomization, the Randomization Form should be completed (Appendix 8).

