## 8. CRITERIA FOR EVALUATION AND ENDPOINT DEFINITION

### 8.1 Primary Endpoint

To determine study feasibility, recruitment, accrual, retention, and adherence rates will be calculated as follows:

**Recruitment.** To determine recruitment rate, we will track number of individuals who met all eligibility criteria and percent who agree to participate.

**Accrual.** Accrual rates will be calculated by calculating the mean number of participants recruited per month.

**Retention.** Study retention will be estimated by the proportion of participants who complete the Week 13 visit. Drop-out is defined as 100% minus the dropout %.

**Adherence.** Intervention adherence will be estimated as the mean percentage of therapy (high-intensity intervention) or check-in (low-intensity intervention) sessions each participant completes.

The Working Alliance Inventory will be summarized with descriptive statistics to describe the therapist-participant relationship as a process measure

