### 13.4 Primary Objective, Endpoint(s), Analysis Plan

For Objective 1.1.1, recruitment, accrual, retention, and adherence rates will be calculated. To determine the recruitment rate, we will track number of eligible participants and percent who agree to participate. Accrual rates will be calculated by calculating the mean number of participants recruited per month. Study retention will be estimated by the proportion of participants who complete the Week 7 and 13 visits. Intervention adherence will be estimated as the mean percentage of therapy or check-in sessions each participant completes. Drop-out is defined as 100% minus the dropout %. 95% confidence intervals will be calculated for each measure to quantify uncertainty in the estimates and to determine if the lower (recruitment, accrual) or upper (retention, adherence) limit would indicate lack of feasibility for future work.

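### Section 13.7 bases retention and accrual on consenters, while sections 3, 7.5 and 13.3 work with randomised participants; the difference can move the 30% drop-out check

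*Combined protocol and SAP*

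**What the plan says.** Section 13.7 is where the plan defines its analysis sets. Recruitment is calculated on all eligible people. For the other three feasibility measures it says: "Accrual, retention, and adherence will be calculated on the participants who consent to participate in the study". Its next sentence uses consenters again for the secondary and exploratory objectives, which are to be analysed by intent to treat.

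The order of steps is set in section 7.4. When consent is taken by phone, "the site must receive the signed full informed consent prior to initiating baseline study activities". Then "Randomization must happen after baseline assessments but within 30 days of screening", and there is a further condition: "The sites must receive the following self-administered completed forms from the participant prior to enrolling and randomizing the participant".

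Elsewhere the plan counts randomised people:

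- Section 7.5: "A participant will not be considered enrolled if they are not randomized to a study arm".
- Section 3 plans recruitment as follows: "Assuming an accrual rate of approximately 8-9 randomized participants per month".
- Section 13.3 computes the drop-out limit with N=90, the number to be randomised, and takes its 20% drop-out allowance from the 45 randomised per group.

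The retention numerator also differs. Section 8.1: "Study retention will be estimated by the proportion of participants who complete the Week 13 visit". Section 13.4, in line with section 5.1: "Study retention will be estimated by the proportion of participants who complete the Week 7 and 13 visits".

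**The concern.** A person can give full consent and still not reach randomisation. The self-report forms may not come back. Section 7.4 also provides for repeating the PHQ-9 and GAD-7 to reassess eligibility when more than 30 days have passed since screening, and exclusion 4.2.1 (current psychotherapy) is dated from randomisation, so eligibility can lapse after consent. Such a person has no arm and no Week 7 or Week 13 visit. No section removes that person from the retention denominator set in 13.7.

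Retention is a primary endpoint, and the 30% drop-out bar in 13.3 is the only numerical feasibility threshold attached to it. Under 13.7 the rate mixes loss before randomisation with loss during the study, although the bar was worked out for the second kind only. Two analysts, one following 13.7 and the other 7.5 and 13.3, could report limits on opposite sides of 30% from the same data. Accrual moves the other way: counting consenters raises it against a target stated in randomised participants.

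**Working it through.** **Inputs.** From section 13.3: N=90, a 30% drop-out bar, an observed drop-out of 22% with a one-sided 95% upper limit of 29.2%, and a planning drop-out of 20% (18 of 90). From section 3: 90 randomised over 11 months. Two assumptions are mine. First, drop-out is 100% minus retention, because the definition printed in 8.1 and 13.4 refers to itself. Second, k, the number who consent but are never randomised, is varied because the documents give no figure.

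**Reproducing the plan's figure.** The one-sided 95% Wald limit is p + 1.645 × √(p(1−p)/n). With p = 0.22 and n = 90: 0.22 + 1.645 × √(0.22 × 0.78/90) = 0.22 + 0.072 = 0.292. This matches the stated 29.2%, so the same formula is used below.

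**Literal reading of 13.7.** With x drop-outs among the 90 randomised and k lost before randomisation, the drop-out rate is (x + k)/(90 + k).

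At the plan's 20% drop-out (x = 18):

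| k | Drop-out | Upper limit |
|---|---|---|
| 0 | 18/90 = 20.0% | 26.9% |
| 2 | 20/92 = 21.7% | 28.8% |
| 4 | 22/94 = 23.4% | 30.6% |
| 5 | 23/95 = 24.2% | 31.4% |
| 10 | 28/100 = 28.0% | 35.4% |

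Smallest k that takes the limit past 30%, for other drop-out counts:

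| Drop-outs among 90 | Limit at k = 0 | k needed | Rate at that k | Limit at that k |
|---|---|---|---|---|
| 10 (11.1%) | 16.6% | 15 | 25/105 = 23.8% | 30.6% |
| 15 (16.7%) | 23.1% | 8 | 23/98 = 23.5% | 30.5% |
| 18 (20.0%) | 26.9% | 4 | 22/94 = 23.4% | 30.6% |
| 19 (21.1%) | 28.2% | 2 | 21/92 = 22.8% | 30.02% |
| 20 (22.2%) | 29.4% | 1 | 21/91 = 23.1% | 30.3% |

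The point estimate itself passes 30% only at k = 13 when x = 18 (31/103 = 30.1%), or k = 11 when x = 20 (31/101 = 30.7%).

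**Randomised denominator.** The limit stays at 26.9% for 18/90 and 29.4% for 20/90, whatever k is.

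**Accrual over 11 months.** 90/11 = 8.2 per month on randomised participants. If 95 consent it is 95/11 = 8.6, and if 100 consent it is 100/11 = 9.1.

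**Numerator.** Someone who misses Week 7 but completes Week 13 is retained under 8.1. Under 5.1 and 13.4 that person is not retained if both visits are required. Those two sections can also be read as asking for one proportion per visit. The documents give nothing from which to size this difference.

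**The case against.** The strongest reply is that context already shows what was meant. Nobody is enrolled until randomised, and section 7.5 starts the study timeline at randomisation, so a Week 13 visit has no meaning for someone never randomised. Section 8.3 applies its lost-to-follow-up rule to enrolled subjects. On this view 13.7 is loosely worded and does not deliberately count early losses as drop-outs. That is plausible, and it is why this is a conflict to reconcile. It does not remove the conflict, because 13.7 names the denominator and no section overrides it.

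Several narrower replies stand in full:

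- Adherence is already tied to the high- and low-intensity groups in 5.2 and 8.1, so a person with no scheduled sessions has no adherence value to average.
- The outcome models in 13.5 contain an intervention-group term. People with no arm cannot enter them, so those effect estimates would not change. The set named for these analyses still needs correcting.
- Baseline forms need not be mailed. They can be completed at the site or collected by phone, and the steps through baseline can share one in-person visit. These routes may keep the loss small.
- Section 13.3 does not size everything on 90 randomised: its recruitment precision uses at least 100 approached, and its accrual precision uses 11 people per month.
- The accrual effect is small. With 95 consenters the monthly figure stays within the planned 8-9.

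A reader might infer from the table that a handful of lost consenters would turn a feasible trial into an infeasible one. The documents do not support that. They give no consent-to-randomisation loss, the result depends on how close drop-out is to the plan's ceiling, and 13.3 says only that a larger study might not be feasible above 30%.

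**Conclusion.** The inconsistency is real and bears on a primary endpoint. Section 13.7 uses consenters for retention and accrual; sections 3, 7.5 and 13.3 use randomised participants, and nothing reconciles them.

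The numerical consequence is conditional on three things: a literal reading of 13.7, drop-out taken as the complement of retention, and an assumed number lost between consent and randomisation. Near the plan's drop-out ceiling, between one and four lost consenters carry the upper limit past 30%. At 15 of 90 it takes 8, and at 10 of 90 it takes 15. Because the bar is a caution and section 13.8 says the intervention-effect analyses are for planning, the harm is a misleading retention figure and an ambiguous feasibility statement, not an automatic stop. The two retention numerators are a secondary inconsistency of unknown size.

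**What to change.** In section 13.7, replace consenters with randomised participants as the set for retention, accrual and the intent-to-treat secondary and exploratory analyses. State adherence on those randomised to stepped care, which agrees with 5.2 and 8.1.

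Report the proportion of consenters who are randomised as a separate recruitment step. Otherwise this loss would fall between the recruitment rate (agreement among the eligible) and retention, and appear in neither.

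Reconcile the retention numerator across 5.1, 8.1 and 13.4. One option is to use Week 13 completion for the 30% drop-out check and report Week 7 completion alongside it.

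The cost is wording in 13.7, plus 5.1, 8.1 and 13.4 for the numerator. No change to data collection is needed.
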